10.2 Endpoints

Generally, for statistical calculation of end of therapy change from baseline, baseline and end of therapy values are defined as follows.

HDSM-Ax and HDSS:

baseline value = average of two screening values, i.e. Visit 1 and Visit 4

end of therapy value = average of Days 41, 42, and 43 measurements, i.e. Visit 11, Visit 12, and Visit 13, respectively.

Gravimetric Sweat Production (both axilla combined):

baseline value = the median of GSP1, GSP2, and GSP3 measurements obtained on Visit 2, Visit 3, and Visit 4, respectively

end of therapy value = the median of GSP4, GSP5, and GSP6 measurements obtained on Visit 11, Visit 12, and Visit 13, respectively.

Primary efficacy endpoint will be defined as:

- 1. The proportion of subjects achieving at least a 1-point improvement in HDSM-Ax from baseline to end of therapy.
- 2. Change of HDSM-Ax from baseline to end of therapy as a continuous measure

Secondary efficacy endpoints will include the following.

- 1. The proportion of subjects achieving at least a 2-point improvement in HDSM-Ax from baseline to end of therapy.
- 2. The proportion of subjects achieving at least a 50% reduction in gravimetrically measured sweat production (both axilla combined) from baseline to end of therapy.
- 3. The absolute change from baseline in gravimetrically measured sweat production to end of therapy.
- 4. The percent change from baseline in gravimetrically measured sweat production to end of therapy.
- 5. The proportion of subjects achieving at least a 1-point improvement in the HDSM-Ax score and at least 50% reduction in gravimetrically measured sweat production from baseline to end of therapy.
- 6. The proportion of subjects achieving at least a 2-point improvement in the HDSM-Ax total score and at least 50% reduction in gravimetrically measured sweat production from baseline to end of therapy.
- 7. The proportion of subjects achieving at least a 2-point improvement in HDSS from baseline to end of therapy.

Page 46 of 65

8. The proportion of subjects achieving at least a 1-point improvement in HDSS from baseline to end of therapy.

Other efficacy endpoints will include:

- 1. The proportion of subjects achieving at least a 1-point improvement in the HDSM-Ax score from baseline to Days 8, 15, 22, 29, 36, 41, 42, 43, and 57.
- 2. Change in HDSM-Ax from baseline to Days 8, 15, 22, 29, 36, 41, 42, 43, and 57 as a continuous measure
- 3. The proportion of subjects achieving at least a 2-point improvement in the HDSM-Ax score from baseline to Days 8, 15, 22, 29, 36, 41, 42, 43, and 57.
- 4. The proportion of subjects achieving at least a 50% reduction in gravimetrically measured sweat production (both axilla combined) from baseline to Days 8, 15, 22, 29, 36, 41, 42, 43, and 57.
- 5. Percent change from baseline in gravimetrically measured sweat production at Days 8, 15, 22, 29, 36, 41, 42, 43, and 57.
- 6. Absolute change from baseline in gravimetrically measured sweat production at Days 8, 15, 22, 29, 36, 41, 42, 43, and 57.
- 7. The proportion of subjects achieving at least a 1-point improvement in the HDSM-Ax score and at least 50% reduction in gravimetrically measured sweat production from baseline to Days 8, 15, 22, 29, 36, 41, 42, 43, and 57.
- 8. The proportion of subjects achieving at least a 2-point improvement in the HDSM-Ax total score and at least 50% reduction in gravimetrically measured sweat production from baseline to Days 8, 15, 22, 29, 36, 41, 42, 43, and 57.
- 9. The proportion of subjects achieving at least a 2-point improvement in HDSS from baseline to Days 8, 15, 22, 29, 36, 41, 42, 43, and 57.
- 10. The proportion of subjects achieving at least a 1-point improvement in the HDSS on Days 8, 15, 22, 29, 36, 41, 42, 43, and 57.
- 11. Change in the modified dermatology life quality index (modified DLQI) from baseline to Day 43 (end of therapy), and Day 57.

10.3 Efficacy Analyses

Descriptive summaries will be provided for all efficacy endpoints by treatment groups at specified time points. Mean, standard deviation, median, minimum and maximum will be reported for continuous variables. Frequencies and proportions will be reported for categorical variables. For continuous endpoints specified in 10.2, change from baseline will be similarly summarized.

Primary Efficacy Analyses

The mean of the items in sections No. 1, 2, and 3 of the HDSM-Ax (11 sub-items in total) will be used for analysis. The mean will be derived by taking the total score and dividing by the number of questions answered. Subjects must answer at least 6 of the 11 sub-items to be evaluable for HDSM-Ax total score.

Page 47 of 65

Change from baseline to end of therapy for the primary efficacy measure of HDSM-Ax will be analyzed both as a continuous measure and as a binary endpoint. As a continuous measure, the HDSM-Ax change scores will be compared between all active treatment groups and the vehicle group by an ANCOVA model adjusting for the baseline HDSM-Ax score. As a binary measure, i.e. achieving a 1-point improvement or not from baseline to end of therapy, a logistic regression will be performed with treatment assignment and baseline HDSM-Ax score as independent variables in the model. As a phase 2 study, a 1-sided p<0.10 in favor of an active treatment will be regarded as a positive sign for further investigation.

Missing data will not be imputed for the primary analyses. As sensitivity analyses, mixed model repeated measures (MMRM) analyses may be performed using all available HDSM-Ax change from baseline data on study days 8, 15, 22, 29, 36, and end of therapy.

Additional Efficacy Analyses

Analyses for secondary and other efficacy endpoints will be similar to the binary HDSM-Ax analysis described above. For gravimetric results analyzed as continuous measures, analyses assuming Normality for the data distribution (i.e. comparing means) and analyses using rank transformed data (i.e. comparing medians) will both be performed. All non-primary analyses will be based on available data only.

In parallel to the traditional statistical analysis, psychometric evaluation of the HDSM-Ax will be carried out to confirm the most appropriate HDSM-Ax scoring algorithm and to examine internal validity, construct validity (i.e., examinations of the magnitude of correlation between the HDSM-Ax total score (Items 1, 2, and 3) and key variables such as; items 4 and 5 of the HDSM-Ax, HDSS and gravimetrically measured sweat production), stability, reliability, ability to detect change, and interpretability of clinical trial results.

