10.5 Sample Size and Power Estimation

For the binary version of the primary endpoint, i.e. proportion of subjects achieving at least a 1-point improvement in HDSM-Ax from baseline to end of therapy, assume the true response rates

Page 48 of 65

to be 75% for each BBI-4000 arm and 50% for vehicle control (based on prior data). With 100 evaluable subjects at a 1:1 ratio for each pairwise comparison between a BBI-4000 arm and the vehicle arm, i.e. 50 evaluable subjects per arm, the power is approximately 0.87 for observing a response rate difference in favor of BBI-4000 at a 1-sided p<0.10 level. To limit the study-wide false positive rate to 0.10, a gate-keeping hierarchical testing algorithm will be employed. That is, the BBI-4000 15% group will be compared to the vehicle first, if the result is favorable with a 1-sided p<0.10, then the BBI-4000 10% group will be compared to vehicle. Similarly, if the BBI-4000 10 % is favorable with a 1-sided p<0.10, then the BBI-4000 5% group will be compared to vehicle.

For the continuous version of HDSM-Ax change from baseline to end of therapy, assume the true mean difference between each BBI-4000 arm and the vehicle arm to be 0.18, with a common standard deviation of 0.36, i.e. an effect size (mean difference/standard deviation) of 0.50. With 100 evaluable subjects at a 1:1 ratio for each pairwise comparison between a BBI-4000 arm and the vehicle arm, the power is approximately 0.89 for observing a difference in favor of BBI-4000 at a 1-sided p<0.10 level. Same as for the binary version of HDSM-Ax, the gate keeping hierarchical testing algorithm will be employed for the continuous data.

Assuming an approximate 10% non-evaluable rate for the ITT primary efficacy analyses, 220 randomized subjects are targeted for enrollment.

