Statistical significance testing will be one-sided as described in Section 7.4.4.1, and performed using $\alpha=0.10$. P-values will be reported for all statistical tests, rounded to four decimal places. P-values less than 0.0001 will be displayed as “<0.0001”; p-values greater than 0.9999 will be displayed as “>0.9999”. Tests of interaction terms, if applicable, will be two-sided and performed using $\alpha=0.10$.

7.1.2 *Standard Calculations*

Where appropriate, the calculated study day of each assessment or event will be presented with the assessment or event date on subject data listings, where study day will be determined as:

- The assessment/event date minus the date of first dose, if the assessment/event date is prior to the date of first dose; and
- The assessment/event date minus the date of first dose, plus one, if the assessment/event date is on or after the date of first dose.

Other variables requiring calculations will be derived using the following formulas:

- **Days:** A duration between two dates expressed in days will be calculated using the following conventions:
 - Later date – earlier date + 1, if the earlier date is on or after the date of first dose of study drug; or
 - Later date – earlier date, if the earlier date is prior to the date of first dose of study drug.
- **Change from Baseline:** Change from baseline will be calculated as the post-baseline value minus the baseline value;
- **Percentage Change from Baseline:** Percentage change from baseline will be calculated as the change from baseline divided by the baseline value, multiplied by 100.
- **Rank Transformation:** All raw data will be ranked together within time point without regard to treatment group, from smallest value to highest value. The smallest observation will be assigned the rank of 1, the second smallest the rank of 2, and so on. Average ranks will be used for tied observations.

Unless otherwise noted, values reported as greater than or less than some quantifiable limit (e.g., “< 1.0”) will be summarized with the sign suppressed in summary tables and figures, using the numeric value reported. Data will display on subject listings to include the sign.

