The primary efficacy endpoint is the change from baseline to the end of therapy in the mean HDSM-Ax score. The primary efficacy endpoint will be analyzed both as a continuous measure and as a binary outcome. As a continuous measure, the HDSM-Ax change scores will be compared between treatment groups in pairwise fashion by an ANCOVA model adjusting for the baseline HDSM-Ax score. The analysis will be performed with no imputation of missing data. As a binary measure, i.e. achieving a ≥ 1 -point improvement or not from baseline to end of therapy, a binary logistic regression will be performed with treatment assignment and baseline HDSM-Ax score as independent variables in the model. Any subject without a definable 1-point improvement (e.g., missing data) between Baseline and End of Treatment will be considered a non-responder. P values will generally be regarded as descriptive and statistical significance will be assessed using a gate-keeping hierarchy as described in Section [7.4.6.5](#) for both the continuous measure and binary data analyses.

The null hypothesis to be tested for the continuous measure is as below:

$$H_0: \mu_A \geq \mu_P;$$

where μ_A and μ_P represent the true underlying mean change scores for Treatment A (active drug) and Treatment P (vehicle), respectively. The alternate hypothesis to be tested is that the true active treatment group mean change score is smaller than the true vehicle group mean change score:

$$H_1: \mu_A < \mu_P;$$

Tested in the logit scale, the null hypothesis for the dichotomous outcome is that the true proportion of subjects with a 1 point or more improvement is lower in the active treatment group:

$$H_0: P_A \leq P_P;$$

The alternate hypothesis to be tested is that the true proportion of subjects with a 1 point or more improvement is higher in the active treatment group:

$$H_1: P_A > P_P;$$

7.4.4.2 *Sensitivity Analysis by Mixed Effects Models*

As a method that is known to be robust to missing data, mixed model repeated measures (MMRM) analyses will also be performed for the primary efficacy endpoint using all available HDSM-Ax change from baseline data on study days 8, 15, 22, 29, 36, and end of therapy. As fixed effects, treatment (active treatment group or vehicle gel), baseline HDSM-Ax score and visit (included in the class statement as a class variable) and baseline*visit interactions will be

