7.4.6.5 Multiple Comparisons/Multiplicity

To limit the study-wide false positive rate to 0.10, a gate-keeping hierarchical testing algorithm will be employed to assess statistical significance regarding the primary analyses for the primary efficacy endpoint, i.e. ANCOVA analyses on change from baseline in HDSM-Ax score. The hierarchy is, the comparison between BBI-4000 15% group and vehicle group will be considered first, if the result is favorable with a 1-sided $p < 0.10$, then the comparison between BBI-4000 10% group and vehicle will be considered. Similarly, if the BBI-4000 10% group is favorable with a 1-sided $p < 0.10$, then comparison between BBI-4000 5% group and vehicle will be considered. The same gate keeping hierarchical testing algorithm will be employed for both the binary data analysis and the continuous measurement analysis.

The primary efficacy analysis will be performed on the mITT population; the PP population will be utilized for selected efficacy analyses. The PP population is described in Section [7.2](#).

7.4.6.6 *Active-Control Studies Intended to Show Equivalence*

This study does not include an active-control product and is not intended to demonstrate equivalence between any two drug products.

7.4.6.7 *Examination of Subgroups*

There are no planned analyses to assess efficacy results by subgroups.

7.5 **Safety Analysis**

Safety analysis will be carried out for the Safety Population, to include all subjects who receive at least one dose of study drug. Subjects who do not complete the study, for whatever reason, will have all available data up until the time of termination included in the analysis. For safety analysis presented by study visit, the baseline value will be defined as the last value reported prior to first study drug administration.

7.5.1 *Extent of Exposure*

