The study phase of each therapy/procedure will be determined programmatically based on start and end dates. A prior therapy/procedure is defined as any therapy/procedure occurring prior to the date of the first dose of study drug. A concomitant therapy/procedure is defined as any therapy/procedure occurring on or after the date of the first dose of study drug. A therapy/procedure may be defined as both prior and concomitant. If it cannot be determined whether a therapy/procedure occurred prior to the start of study drug dosing due to partial or missing, it will be considered a prior therapy/procedure. Likewise, if it cannot be determined whether a therapy/procedure occurred after the start of study drug dosing, it will be considered concomitant. Therapies and procedures will be reported in a subject listing, and identified as prior or concomitant, and as a therapy or a procedure.

7.6 **Determination of Sample Size**

For the binary version of the primary endpoint, i.e., proportion of subjects achieving at least a 1-point improvement in HDSM-Ax from baseline to end of therapy, the true response rates will be assumed to be 75% for each BBI-4000 arm and 50% for vehicle control (based on prior data). With 100 evaluable subjects at a 1:1 ratio for each pairwise comparison between a BBI-4000 arm and the vehicle arm, i.e., 50 evaluable subjects per arm, the power is approximately 0.87 for observing a response rate difference in favor of BBI-4000 at a 1-sided $p < 0.10$ level.

For the continuous version of HDSM-Ax change from baseline to end of therapy, the true mean difference between each BBI-4000 arm and the vehicle arm will be assumed to be 0.18, with a common standard deviation of 0.36, i.e., an effect size (mean difference/standard deviation) of

0.50. With 100 evaluable subjects at a 1:1 ratio for each pairwise comparison between a BBI-4000 arm and the vehicle arm, the power is approximately 0.89 for observing a difference in favor of BBI-4000 at a 1-sided $p < 0.10$ level.

Assuming an approximate 10% non-evaluable rate for the mITT primary efficacy analyses, 220 randomized subjects are targeted for enrollment.

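### Protocol 10.3 reads a one-sided p<0.10 at any dose as a positive sign with no dose order, and nothing ties that sentence to the 15%, 10%, 5% gate of protocol 10.5 and the SAP; power under the gate is not given for 10% and 5%

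*Protocol*

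**What the plan says.** **Protocol 10.3 (Efficacy Analyses).** The HDSM-Ax change scores "will be compared between all active treatment groups and the vehicle group" by ANCOVA, and the 1-point response is analysed by logistic regression. The section then gives its criterion for a favourable result: "a 1-sided p<0.10 in favor of an active treatment will be regarded as a positive sign for further investigation". It sets no order among doses and does not refer to 10.5.

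**Protocol 10.5 (Sample Size and Power Estimation).** "To limit the study-wide false positive rate to 0.10, a gate-keeping hierarchical testing algorithm will be employed". The 15% dose is compared with vehicle first. The 10% dose is compared only if 15% has a favourable one-sided p<0.10, and 5% only if 10% does. The same section gives power of about 0.87 for the binary version. For the continuous version, "the power is approximately 0.89 for observing a difference in favor of BBI-4000 at a 1-sided p<0.10 level". Both figures are for a single comparison with 50 evaluable subjects per arm.

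**SAP.** Section 7.4.4.1 says "P values will generally be regarded as descriptive and statistical significance will be assessed using a gate-keeping hierarchy". Section 7.4.6.5 repeats the order of doses and adds: "The same gate keeping hierarchical testing algorithm will be employed for both the binary data analysis and the continuous measurement analysis". Section 7.1.1 says "P-values will be reported for all statistical tests, rounded to four decimal places". Section 7.6 repeats the power figures, again "With 100 evaluable subjects at a 1:1 ratio for each pairwise comparison between a BBI-4000 arm and the vehicle arm", and does not mention the gate. Section 7.7 lists seven changes from the protocol; none concerns the 10.3 sentence.

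**The concern.** The two protocol sections use the same threshold on the same primary endpoint but differ on which doses may be judged by it. Suppose 15% misses and 10% has p=0.04. Under 10.3 the 10% dose shows a positive sign. Under 10.5 it is never compared.

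The SAP settles what counts as statistically significant. It does not say whether the protocol's positive-sign criterion still stands, although its Introduction says that changes from the protocol's statistical methods will be explained there. The p-values needed to apply either rule will be printed for every dose.

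What is at stake is the reading of two of the three doses in a study meant to indicate which concentrations of the new formulation to pursue. A choice between the rules made after the p-values are seen would be post hoc. A reader of 10.5 or SAP 7.6 may also take 0.87 and 0.89 as the chance of success for each dose, which under the gate is true of 15% only.

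**Working it through.** **Inputs.** From protocol 10.5: one-sided α = 0.10 (critical value 1.2816); 50 evaluable per arm; response 75% in each active arm and 50% on vehicle; mean difference 0.18, SD 0.36. Allocation is 1:1:1:1 (protocol 2), so all three comparisons share one vehicle arm and their statistics have correlation 0.5. Baseline adjustment is left out, as in the plan's own power figures.

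**1. Reproduce the stated powers.**
- Continuous: 0.18 / (0.36 × √(2/50)) = 0.18 / 0.072 = 2.5, and Φ(2.5 − 1.2816) = 0.888. The noncentral t gives 0.886. Both agree with 0.89.
- Binary, with continuity correction: pooled SE = √(0.625 × 0.375 × 2/50) = 0.0968; unpooled SE = √((0.1875 + 0.25)/50) = 0.0935; correction = 0.02. Then Φ((0.25 − 0.02 − 1.2816 × 0.0968)/0.0935) = Φ(1.13) = 0.871. Exact power of Fisher's test is 0.864. Both agree with 0.87. Without the correction the formula gives 0.911.

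Both stated figures are therefore powers for one comparison with no gate.

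**2. Chance of any false positive with no effective dose, one endpoint version.**
- No gate: P(at least one of three statistics exceeds 1.2816), correlation 0.5, is 0.218. By test, it is 0.212 with the unadjusted Wald logistic test and 0.153 with the conservative Fisher test. Independent comparisons would give 1 − 0.9³ = 0.271.
- Gate: only a success at 15% opens it, so the rate is 0.10.

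**3. Power under the gate.** For 15%, 10% and 5% this is P(15% succeeds), P(15% and 10% succeed) and P(all three succeed), with equal true effects:

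| Version and method | Ungated, each dose | Gated 15% / 10% / 5% |
|---|---|---|
| Continuous, t test | 0.89 | 0.89 / 0.81 / 0.76 |
| Binary, continuity-corrected | 0.87 | 0.87 / 0.79 / 0.73 |
| Binary, Fisher exact | 0.86 | 0.86 / 0.78 / 0.72 |
| Binary, unadjusted Wald logistic | 0.90 | 0.90 / 0.84 / 0.79 |

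The binary rows differ only by test. The continuity-corrected row is the one consistent with the plan's 0.87.

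**4. How often the two rules disagree (continuous, simulated trials with a shared vehicle arm).**
- Equal effects of 0.5 SD: 10% has p<0.10 but is blocked in 0.887 − 0.812 = 0.075 of trials, and 5% in 0.887 − 0.757 = 0.130. These overlap; at least one dose is affected in about 0.15 of trials.
- The 15% dose misses in 0.113 of trials. Given that, 10% or 5% has p<0.10 in 0.83 of them, which is 0.113 × 0.83 = 0.09 of all trials.
- Effects falling with dose (assumed 0.5/0.35/0.2 SD for 15%/10%/5%): the rules disagree on at least one dose in about 0.09 of trials. The conditional figure after a miss at 15% drops from 0.83 to about 0.37.

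**The case against.** The strongest reply is that the SAP already has one rule. Section 7.4.4.1 makes the gate the test of significance and treats p-values as otherwise descriptive; 7.4.6.5 gives the order for both versions of the endpoint. Protocol 10.3 speaks of a signal in a phase 2 study and claims neither significance nor error control. One can read 10.3 as setting threshold and direction and 10.5 as setting order. The phrase about comparing all active groups describes the model, not a decision rule.

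Much of this stands. A reader might infer that the plan contains two competing significance tests. The documents do not support that: there is no conflict inside the SAP, and what remains is one protocol sentence left unreconciled. The conciliatory reading is possible, but neither document states it.

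A reader might also infer that the power figures are wrong, or that no rule gives both the stated power and the 0.10 limit. Both powers are correct and labelled pairwise, and under the gate 15% has the stated power with the 0.10 limit for its endpoint version. What is missing is the gated power for 10% and 5%.

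Nor is it safe to say that the rules clash in most trials where 15% misses. The 83% behind that statement needs equal effects at all doses. Protocol 10.5 assumes this for sample size, but the protocol's account of study CL-201 reports greater improvement at 15% than at lower concentrations.

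Finally, printing every p-value is ordinary once the text calls them descriptive, so marking unreached doses in the table shells is optional.

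**Conclusion.** The point holds as a gap between protocol 10.3 and the gate, together with an omission in the power statement. Should 15% miss and a lower dose have p<0.10, the protocol gives two readings of that dose and the SAP does not withdraw either.

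Applied without the gate, the 10.3 rule has a false positive rate of about 0.22 on one endpoint version (0.15 with Fisher's test), not 0.10. Under the gate, power for 10% and 5% is about 0.81 and 0.76 (continuous) or 0.79 and 0.73 (binary, by the method that reproduces 0.87). The rules would disagree on at least one dose in about 0.15 of trials with equal effects, and in about 0.09 with the assumed falling effects.

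These figures rest on 50 evaluable subjects per arm, the response rates and effect size of protocol 10.5, a shared vehicle arm and no baseline adjustment. They concern one endpoint version at a time. A reader might infer that the gate secures 0.10 for the whole study. It does so within a version; if a success on either version may count, the rate lies between 0.13 and 0.19 for an assumed correlation between versions of 0.9 down to 0.

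**What to change.** Before unblinding:

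1. **Protocol 10.3:** add that a one-sided p<0.10 counts as positive only for a dose reached by the 10.5 gate, and that p-values for other doses are descriptive. Note this clarification in SAP 7.7.
2. **Protocol 10.5 and SAP 7.6:** label 0.87 and 0.89 as ungated pairwise power and add the gated power for 10% and 5%, naming the test. For example, 0.81 and 0.76 for the continuous version (t test) and 0.79 and 0.73 for the binary version (continuity-corrected). If the Wald logistic or Fisher figures are used instead, the 15% figure should come from the same method.
3. **If the any-dose signal is what the sponsor wants:** say in both documents that it is not error-controlled and give its rate of about 0.22 per endpoint version.

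A footnote in Tables 14.2.1.3 and 14.2.1.7 marking doses the gate did not reach would help but is not essential.

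The cost is a few sentences, with no extra patients and no change to any test. If the gate is kept, a lower dose can no longer be called positive after a failed 15%, and the power stated for 10% and 5% will be lower than a reader may now assume.
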